#### 3.4.3 *Blood results*

At each follow-up visit, results for creatinine and therapeutic drug level monitoring will be recorded, as well as a full blood count, lipid profile (total cholesterol, HDL-cholesterol and triglycerides if available) and urinary protein:creatinine ratio at certain visits. These will be copies of results of routine clinical tests requested by the managing team. See Appendix 6: Schedule of study procedures.

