 - k. Proteinuria (compared by calculating ratio of geometric means) [at 3 and 6 months post-randomization only]. If albumin:creatinine ratio (ACR) value is available but not protein:creatinine ratio (PCR) for a given time-point, then it will be converted to PCR by the formula PCR = ACR x 1.6
 - l. Total cholesterol, HDL-cholesterol, non-HDL-cholesterol and triglyceride concentrations, and use of lipid-lowering therapy [at 6 months post-randomization only]
 - iv. Tolerability

- a. Reasons for stopping allocated treatment subdivided into suspected serious adverse reactions, serious adverse events (subdivided as in iii.e above), non-serious adverse reactions (including proteinuria, deteriorating graft function and other NSARs in same categories as SAEs) and other reasons (patient wishes or other)

These analyses will be conducted when all participants have completed 2 years and at a median follow-up of 5 years after transplantation. Participants will be censored at the date at their date of death or the date on which they were last known to be alive (based on flagging with the Office for National Statistics) once 2 (or 5) years have elapsed after the last patient was transplanted.

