3.1 Methods of analysis

The fundamental assessments of efficacy and safety will involve comparisons among all randomized patients in their originally allocated treatment group (i.e. “intention to treat” analyses).^{1, 2} Analyses of categorical outcomes will be based on the first relevant unrefuted event of a particular type (i.e. either confirmed or not refuted during the adjudication process). All time-to-event analyses will be based on the first relevant event, and will use log-rank methods to calculate average event rate ratios (95% confidence intervals) and their associated 2-sided P-values.^{2, 4} Comparisons of continuous outcomes will adjust for the baseline value if available, otherwise two-sample t-tests will be used.

The primary comparison between treatment groups of mean follow-up eGFR at 2 years post-transplantation (ie, on average 18 months post maintenance randomisation) will use analysis of covariance (ANCOVA), adjusted for the baseline value.⁵ The baseline creatinine value used will be the latest value available prior to the maintenance randomisation (including a value from a sample

taken on the day of that randomisation). Any value within 6 months of the anniversary of the date of transplantation will be considered as that year's value. If multiple results are available within this window, the one closest to the anniversary date will be used.

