3.2 Missing data

It is likely that values of creatinine will be missing at random (as they will be collected via the UK Transplant Registry and it is very unlikely that their randomized allocation would affect whether a hospital provides data to the registry). Baseline characteristics of those participants with available and those participants with missing data will be compared to identify any characteristics associated with missingness. The amount of missing data at various timepoints after transplantation will be displayed graphically.

Missing eGFR values will be imputed using a multiple imputation model, using baseline covariates of:

- Age (calendar year)
- Sex
- Type of transplant (living donor, donor after brain death and donor after cardiac death)
- Donor age (calendar age)
- Proteinuria at baseline (in categories: ≤ 30 mg/mmol, >30 mg/mmol)
- Available eGFR values (both before and after the value that requires imputation) of creatinine (hence eGFR) will be used as time-varying covariates (as exact values [to 1 decimal place]). Values before the maintenance randomisation will not be considered, nor any values on or after the date of failure of the transplant.
- Any characteristics associated with missingness

The imputation model will be stratified by the induction and maintenance therapy randomized allocations.

20 imputed datasets will be generated and then analysed using methods described in section 3.1.⁶ These 20 results will then be combined in order to produce an overall result using standard procedures.⁷ A complete case analysis will be conducted for comparison, but the primary emphasis will be placed on results after multiple imputation.

Any participant whose transplant has failed will be given an eGFR of 0 mL/min/1.73m² for all analyses after the date of failure. Sensitivity analyses will be conducted to vary this value of eGFR for failed transplants (range 0-10 mL/min/1.73m²). Participants who have died will have eGFR values imputed as for other missing values (and a sensitivity analysis conducted with 0 imputed for any such participants and if such participants are excluded from the analysis).

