Missing values of tacrolimus or sirolimus will also be imputed for any timepoint for which a value is expected but missing. The baseline variables used to impute missing values will include age, sex, type of transplant, donor age and any available values (as exact values to 1 decimal place) that occur after the maintenance randomisation but before failure of the transplant.

Missing values of urine protein:creatinine ratio will be imputed using baseline age, sex, type of transplant, randomized treatment allocations, available PCR values, angiotensin converting enzyme inhibitor or angiotensin receptor blocker use at baseline, diabetes status and cause of kidney

disease. Missing values for lipid fractions will be imputed using baseline age, sex, randomized treatment allocations, PCR at baseline, diabetes status and statin use at baseline.

All multiple imputation analyses will be implemented using SAS procedure MI. The expectation-maximization algorithm (which assumes a multivariate normal distribution) will be used to impute values (as eGFR is a continuous variable with an approximately normal distribution).

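### Missing lipid values are imputed with no lipid measurement in the model, although the lipid comparison adjusts for baseline lipid: this loses precision when baseline lipids are mostly available, and biases the result only if testing depends on earlier lipids differently by arm

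*SAP*

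**What the plan says.** - **Outcome.** SAP section 2.2, item iii.l: "Total cholesterol, HDL-cholesterol, non-HDL-cholesterol and triglyceride concentrations, and use of lipid-lowering therapy [at 6 months post-randomization only". Protocol section 2.1 names hyperlipidaemia among the secondary objectives, and section 1.3 describes it as a recognised side effect of sirolimus.
- **Analysis.** SAP section 3.1: "Comparisons of continuous outcomes will adjust for the baseline value if available, otherwise two-sample t-tests will be used".
- **Imputation.** SAP section 3.2: "Missing values for lipid fractions will be imputed using baseline age, sex, randomized treatment allocations, PCR at baseline, diabetes status and statin use" at baseline. The method is SAS procedure MI under a multivariate normal model. Section 3.2 does not say whether the lipid fractions go into one run, or how non-HDL is obtained.
- **The other lists in section 3.2.** The PCR list includes "randomized treatment allocations, available PCR values". The drug-level list includes "any available values (as exact values to 1 decimal place) that occur after the maintenance randomisation but before failure of the transplant". The eGFR list uses available eGFR values after the maintenance randomisation, and adds any characteristic found to be associated with missingness. The lipid list has no such catch-all.
- **Number of imputations and complete-case comparison.** "20 imputed datasets will be generated and then analysed using methods described in section 3.1" stands in the eGFR part of section 3.2, as does the planned complete-case comparison. Neither is stated for lipids.
- **Data source.** Protocol section 3.4.3 records a "lipid profile (total cholesterol, HDL-cholesterol and triglycerides if available", at certain visits only, copied from routine tests that the managing team chose to request. Treatment is open-label (Protocol section 2.2).
- **Timing.** In Protocol Appendix 6 the lipid row has three marks. Their alignment is unclear, but the spacing fits discharge, month 6 and month 12. The narrative list of discharge tests (Protocol section 3.3.5) does not name lipids.

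**The concern.** An imputation model should contain every variable in the analysis model. Here the baseline lipid may be in the analysis but is not in the imputation. An imputed 6-month value is then unrelated to the patient's own baseline lipid, apart from what age, sex, PCR, diabetes and statin use convey. Two things follow.

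First, the imputed patients weaken the correlation between baseline and follow-up, so the adjustment removes less variance than it would among the observed patients alone.

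Second, if the decision to test depends on earlier lipids, and does so differently in the two arms, the model lacks the variable needed to correct for it. SAP section 3.2 argues that data are missing at random only for creatinine from the registry. It makes no such argument for lipids, which come from tests requested by unblinded clinicians.

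At stake is the estimate of a known sirolimus effect on a secondary outcome.

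**Working it through.** The documents give no lipid sample size, SD, correlation or missing rate, so there is no figure of the plan to reproduce. The values below are assumptions, shown over ranges.

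**1. Precision, baseline lipid complete and adjusted for.** Let f be the share of follow-up lipids observed (missing at random), rho the correlation of baseline with follow-up, and suppose the listed covariates predict little. Then

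Var(imputation without baseline lipid, then ANCOVA) / Var(complete-case ANCOVA) = [1 - rho² f² (2 - f)] / (1 - rho²).

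With rho = 0.6 and f = 0.7: rho² f² (2 - f) = 0.36 × 0.49 × 1.3 = 0.229. The variance ratio is 0.771/0.64 = 1.204, and the standard error (SE) ratio is √1.204 = 1.097. The SE ratio over the range:

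| rho | 90% observed | 80% | 70% | 50% |
|---|---|---|---|---|
| 0.3 | 1.005 | 1.011 | 1.018 | 1.030 |
| 0.6 | 1.030 | 1.063 | 1.097 | 1.163 |
| 0.8 | 1.093 | 1.188 | 1.283 | 1.453 |

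The ratio does not depend on sample size.

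**2. Reported intervals.** Simulation with 200 per arm, SD 1, a true effect of 0.4 SD, covariates explaining about 6% of lipid variance, 20 imputations and Rubin's rules. Mean reported SE at 70% observed:

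| rho | Planned imputation | Complete-case ANCOVA | Interval wider by |
|---|---|---|---|
| 0.3 | 0.118 | 0.114 | about 3% |
| 0.6 | 0.112 | 0.096 | about 17% |
| 0.8 | 0.105 | 0.072 | about 46% |

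These exceed the ratios in step 1 because Rubin's variance is itself too large when the two models disagree. At rho 0.8 the reported SE is 0.1048 and the actual sampling SE 0.0947. With baseline lipid added to the imputation model, the SE at rho 0.6 falls from 0.112 to 0.097.

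**3. Where the loss disappears.** With a t-test in place of baseline adjustment the SEs are 0.120 and 0.120. With 30% of baseline lipids missing as well as 30% of follow-up values, planned imputation against complete-case ANCOVA gives 0.119 v 0.137 at rho 0.3 (imputation better), 0.117 v 0.114 at rho 0.6 (near parity) and 0.116 v 0.086 at rho 0.8 (imputation worse).

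**4. Bias, in SD units, at rho 0.3, 0.6 and 0.8.**

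- Testing 90% in one arm and 50% in the other, unrelated to lipid level: 0.000, -0.003 and +0.010 (Monte Carlo error about 0.005). Allocation is in the imputation model, so a difference in rate alone does no material harm.
- Testing dependent on baseline lipid in the same way in both arms: at most 0.005.
- Testing dependent on baseline lipid in the control arm only: -0.07, -0.15 and -0.21. Complete-case ANCOVA gives 0.00. Adding baseline lipid to the imputation model gives 0.00 at rho 0.6 and 0.8.

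The last result has a simple form. Untested control patients are filled in at the level of the tested ones, so the bias is about -rho × d, where d is the amount (in SD) by which the baseline lipid of tested control patients exceeds their arm's mean. Here d is 0.07/0.3 = 0.23, 0.15/0.6 = 0.25 and 0.21/0.8 = 0.26, about a quarter of an SD. Against the assumed effect of 0.4 SD the dilution is 0.07/0.4 = 18%, 0.15/0.4 = 38% and 0.21/0.4 = 53%.

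**The case against.** Four points can be made for the plan.

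- **The contrast with the other lists is weaker than it looks.** The eGFR and drug-level lists exclude values before the maintenance randomisation. Lipids are compared at one time point, so under that convention no other time point's lipid value is left to include. This stands: only the PCR list clearly admits a baseline value of its own variable. The case rests on the mismatch with section 3.1, not on inconsistency among the lists.
- **Imputation need not be worse than no imputation.** This stands, as step 3 shows. A reader might infer a general loss of precision, but baseline lipids are routine results recorded where available, and the documents do not say how complete they are.
- **Unequal testing between open-label arms does not by itself bias the result.** This stands too. A reader might infer otherwise from the open-label design, but allocation is a predictor in the model. The harmful pattern, dependence on earlier lipids that differs by arm, is plausible and nowhere shown.
- **The fractions may inform each other.** If all fractions enter one run of the procedure, an observed total cholesterol helps to fill a missing HDL, and non-HDL may simply be computed by subtraction. A reader might infer that the plan will generate non-HDL values above the measured total. That happens only if the fractions are imputed separately and non-HDL is drawn directly, and the SAP states neither. What remains is a request to say which is meant.

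None of this puts the baseline lipid into the imputation list. The eGFR catch-all does not extend to lipids, and the complete-case comparison that would reveal a discrepancy is promised only for eGFR.

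**Conclusion.** The point holds in conditional form. Followed as written, section 3.2 leaves out of the lipid imputation model a covariate that section 3.1 puts into the lipid analysis wherever it is available.

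If baseline lipids are mostly available, intervals are wider than with complete-case ANCOVA: about 3%, 17% and 46% at correlations of 0.3, 0.6 and 0.8 with 70% of follow-up observed. Those inputs are assumptions. The loss is negligible at low correlation or with a t-test, and its direction can reverse if many baseline lipids are missing.

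Bias of about -0.07 to -0.21 SD belongs to one assumed scenario, in which testing depends on earlier lipids in one arm only. The documents make that possible but do not show it.

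The outcome is secondary, and the primary eGFR imputation is untouched. The point still merits a change to the SAP, because the remedy is nearly free and protects against both problems.

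**What to change.** Amend the lipid sentence in SAP section 3.2 as follows:

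1. Impute total cholesterol, HDL and triglycerides jointly. Keep the listed covariates and add the available lipid values: the baseline value before the maintenance randomisation, the discharge value where recorded, and the other fractions from the same visit.
2. Derive non-HDL as total minus HDL after imputation.
3. State that the complete-case comparison covers lipids.

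Using values from before the maintenance randomisation departs from the rule set for eGFR and drug levels. The SAP should say so and give the reason: lipids have a single follow-up time point, and the baseline value is in the analysis model.

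The cost is a sentence or two in the SAP and a few more variables in the imputation code. No new data are needed.

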3.3 Allowance for multiplicity of comparisons

No allowance will be made for multiplicity testing in the primary comparison. For secondary and, particularly, tertiary comparisons, allowance in their interpretation will be made for multiple hypothesis testing,^{1, 2} taking into account the nature of events (including timing, duration and severity) and evidence from other studies. In addition to the pre-specified comparisons, many other analyses will be performed with due allowance for their exploratory and, perhaps, data-dependent nature. Conventionally, two-sided P-values (2P) <0.05 are often described as “significant”. But, the larger the number of events on which a comparison is based and the more extreme the P-value (or, analogously, the further the lower limit of the confidence interval is from zero) after any allowance has been made for the nature of the particular comparison (i.e. primary, secondary or tertiary; pre-specified or exploratory), the more reliable the comparison and, hence, the more definite any finding will be considered.

3.4 Tests for heterogeneity of effects

When a number of different subgroups are considered, chance alone may lead to there being no apparent effect in several subgroups in which the effect of treatment really is about the same as is observed overall. In such circumstances, “lack of direct evidence of benefit” is not good “evidence of lack of benefit”, and clearly significant overall results would provide strong indirect evidence of benefit in some small subgroups where the results, considered in isolation, are not conventionally significant (or, even, perhaps, slightly adverse).^{1, 2, 8} Hence, unless the proportional effect in some specific subcategory is clearly different from that observed overall, the effect in that subcategory is likely to be best estimated *indirectly* by applying the proportional effect observed among all patients in the trial to the absolute risk of the event observed among control patients in that category.⁸ Tests for heterogeneity of the proportional effect on particular outcomes in specific subgroups will be used with allowance for multiple comparisons and for other differences between the subgroups to determine whether the effects in those subgroups are clearly different from the overall effect. If such subgroups can be arranged in some meaningful order then assessment of any trend in the proportional effects on outcome will be made.

4 References

